**11.10 \* Will samples be coded?**

Yes  No

If Yes, Please describe coding scheme consistent with GCP. If samples will not be coded, please provide justification for this proposed departure from GCP practice.

Samples will be coded utilizing the IRB number of the study, followed by the cohort (M= metabolic H= healthy control) and a sequential 3 digit number that contains no identifiers. For example:

UAN-xxxx-M- 001, UAN-xxxx-M-002, etc.

UAN-xxxx-H- 001, UAN-xxxx-H-002, etc.

**12.0  
Subjects of Study****12.1 Specify age range of subjects:**

\* Minimum Age:

18

Maximum Age:

65

Please note: If age of subjects indicated is less than 18 years old, you will be prompted to attach a Pediatric Assent form later on in the submission process. A link to the Pediatric Assent form can be found in the Help link to the right, or this form can be downloaded later on in the submission process.

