To support our hypothesis, several studies have demonstrated that during the 2009 influenza H1N1 pandemic, obesity was associated with more severe infection and death (6, 14). The mechanism is likely immune mediated but has not been determined yet (15). Also, it has been reported that obese people might be less protected by influenza vaccination (7). The area of systems biology has considerably contributed to a better understanding of vaccine efficacy (10, 16). Gene expression studies using peripheral blood can predict vaccine response to influenza (10, 11). High vaccine response correlates with the expression of interferon signaling (genes like STAT1, IRF9) and antigen processing and presentation. To test our hypothesis, we contacted the authors of a study published in Cell in 2014 (12) and obtained the BMI of the patients. The study demonstrated the ability to predict the influenza vaccine response using several parameters. We focused on the immune response based on antibody titers and the gene expression profile at D0 and D1. We separated the individuals in 2 groups: one group of lean (BMI<25) and one group overweight and obese (BMI>25). The two groups contained 25 and 17 individuals respectively. We observed a trend towards an inverse correlation of the immune response to influenza vaccine with increasing BMI. Also, we analyzed the differential gene expression profile between D0 and D1 between the two groups. JUN Kinase, Stat1 and IRF1 were among the most up-regulated genes in the lean group but not in the overweight and obese group. When comparing the two groups using ingenuity pathway analysis, the role of PKR in interferon response, Toll like receptor signaling, Natural killer cell signaling were more activated in the lean group compare to the overweight and obese group. These results indicated that the innate immune response induced by the vaccine might be attenuated in the overweight and obese group. BMI was the only factor used for this analysis and we did not have access to any metabolic marker. Obesity is not necessarily associated with an unhealthy metabolic status. Therefore, we would now like to focus on metabolic syndrome as it better correlate with an unhealthy metabolic status. Our aim is to determine if metabolic syndrome attenuates the immune protection induced by the vaccine and establish the molecular mechanism of antiviral immune deficiency associated with metabolic syndrome. We would like to know if differences between people with and without metabolic syndrome can be seen at the molecular level and correlate with differences in antibody titers. We believe our study will contribute to 1/ better understand vaccine efficacy 2/ establish if the low-grade chronic inflammation associated with metabolic syndrome impacts the systemic immunity against viral infection.

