**11.4 \* Aim(s)**

Indicate how you will *address the hypothesis* (e.g., to compare groups, to estimate a parameter, to ascertain feasibility). Since the sample size determination is usually based on the primary aim only, the primary aim should be sufficient to justify the study.

Antibody response post influenza vaccine will be compared between subjects with the metabolic syndrome and healthy lean controls

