**11.5 \* Primary Outcome(s)**

Indicate which *variable(s)* will be assessed to judge the primary specific aim. Give measurement units, if applicable.

Antibody titers and vaccine response (hemagglutinin)

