**RESEARCH LABS**

**Analyze blood sample and serum for evaluation of the immune response to influenza:****1/ Hemagglutination inhibition assay**

Determine antibody titers against each strain of influenza included in the quadrivalent 2016-2017 vaccine: A/California/7/2009 (H1N1); A/Hong Kong/4801/2014 (H3N2); B/Brisbane/60/2008(B/Victoria lineage); B/Phuket/3073/2013 (B/Yamagata lineage) as described in similar studies (10, 11).

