**Neutralization assay**

Determine the presence of specific neutralizing antibodies to influenza viruses in human sera following the protocol described by the WHO.

[http://www.who.int/influenza/gisrs\\_laboratory/2010\\_12\\_06\\_serological\\_diagnosis\\_of\\_influenza\\_by\\_microneutralization\\_assay.pdf](http://www.who.int/influenza/gisrs_laboratory/2010_12_06_serological_diagnosis_of_influenza_by_microneutralization_assay.pdf)

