**11.8 \* Data Analysis**

Describe method(s) of data analysis. Include the role of external collaborators as appropriate.

As per recommended by the food and drug administration (17), the hemagglutination inhibition (HI) antibody assay has been used to assess vaccine activity and may be appropriate for the evaluation of the pandemic influenza vaccine. Appropriate endpoints may include: 1) the percentage of subjects achieving an HI antibody titer  $\geq 1:40$ , and 2) rates of seroconversion, defined as the percentage of subjects with either a pre-vaccination HI titer  $< 1:10$  and a post vaccination HI titer  $> 1:40$  or a pre-vaccination HI titer  $\geq 1:10$  and a minimum four-fold rise in post-vaccination HI antibody titer. Previous study have built models using both HAI and neutralization assays to determine vaccine responsiveness.

The RNA-seq analysis will be run with the help of the Genome resource center as well as the expertise of [name] listed as a collaborator of this project.

**11.9 \* Explain the rationale for the choice of statistical measures and the number of subjects proposed for the study, including the power calculations when applicable.**

Since no preliminary data is available to estimate the percentage of participants achieving a determined level for the HI antibody titer and the rate of seroconversion for each group (healthy volunteers and metabolic syndrome participants) we provide an estimation of the minimum effect size for the sample size selected is able to detect. For a sample size of 40 participants, 20 at each group, a 95% significant Chi-square test will be able to detect an effect size equal or larger than 0.56 with 0.8 power. It means that a Chi-square test will be able to detect independence between groups if the distance between the observed odd ratio is larger than 1.56.

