**Statistical Analysis**

To compare the means of antibody titers between groups (healthy volunteers and metabolic syndrome participants) a t-test at 95% significance level will be performed if the data follows a normal distribution, otherwise a non parametric Wilcoxon-Mann-Whitney test will be used.

A Chi-square test at 95% significance level will be used for the comparison of percentage of participants achieving a determined level for the HI antibody titer and rates of seroconversion. On that case if any observed frequency is smaller than 5 Fisher exact test will be used instead of Chi-square.

Expression values will be modeled using mixed-effect models, with group as fixed factor, and a random effect for each participant. FCHs for the comparisons will be estimated, and hypothesis testing conducted.

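### Section 11.10 writes the compared cohort (M or H) into every sample code, and the plan describes no re-coding or masked reading before the HI and neutralization assays

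*Combined protocol and SAP*

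**What the plan says.** Section 11.10 builds the code from the study's IRB number, "followed by the cohort (M= metabolic H= healthy control) and a sequential 3 digit number that contains no identifiers". Its examples print M or H, and no sample type is exempted.

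The letter marks the groups of the primary aim (11.4): "Antibody response post influenza vaccine will be compared between subjects with the metabolic syndrome and healthy lean controls". The expected direction is in 11.1: "Our aim is to determine if metabolic syndrome attenuates the immune protection induced by the vaccine".

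The primary outcome (11.5) is "Antibody titers and vaccine response (hemagglutinin"). The Research Labs part of 11.7 ties this to the HI assay: "Determine antibody titers against each strain of influenza included in the quadrivalent 2016-2017 vaccine". It adds a neutralization assay: "Determine the presence of specific neutralizing antibodies to influenza viruses in human sera following the protocol described by the WHO". Section 11.8 gives two HI endpoints, the share at or above 1:40 and "rates of seroconversion, defined as the percentage of subjects with either a pre-vaccination HI titer" below 1:10 with a post-vaccination titer above 1:40, or a pre-vaccination titer of at least 1:10 with a four-fold rise. The Statistical Analysis text under 11.9 adds a t-test or Wilcoxon test "To compare the means of antibody titers between groups".

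The laboratory text in 11.7, the analysis text in 11.8 and 11.9, and the monitoring text in section 23 do not mention a second code, masked readers or a titer lock. The blinding field (10.1) has no legible tick; its free text says only that all participants are vaccinated.

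**The concern.** The coding rule protects personal identity, but it discloses the one attribute an assay reader should not know. Participants and clinic staff cannot be masked to metabolic status. Laboratory staff can be, and nothing in the plan provides for it.

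A titer involves judgement at three points: reading the endpoint dilution, deciding whether to repeat a discordant well, and deciding whether to exclude a result. If the group is visible and the expected direction is known, each decision can depend on group. The comparison is not randomized and has 20 per group, so a small systematic shift adds directly to the contrast, and analysis cannot remove it afterwards. Mean titers, the share at or above 1:40 and seroconversion are all exposed, though not equally.

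**Working it through.** The plan gives no figure to reproduce: no titer SD and no reading error. The case rests on the text above. The calculations only show how much a group-dependent reading could matter, for one strain at one time point.

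**Inputs.** From the plan: 20 per group (11.9), a 5% level (taken as two-sided), the 1:40 threshold, the seroconversion rule, and chi-square replaced by Fisher if any observed count is below 5. Assumed: log2 titers, SD 1.0 to 2.5, no true difference, two-fold dilution steps.

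**Mean titers.** Two-sample t-test, 38 df, noncentrality = shift / (SD × √(2/20)). For a shift of 0.25 step and SD 1.0: 0.25 / (1.0 × 0.316) = 0.791, giving a rejection rate of 12.0%.

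| Shift (steps) | SD 1.0 | SD 1.5 | SD 2.0 | SD 2.5 |
|---|---|---|---|---|
| 0.10 | 6.1% | 5.5% | 5.3% | 5.2% |
| 0.25 | 12.0% | 8.1% | 6.7% | 6.1% |
| 0.50 | 33.8% | 17.7% | 12.0% | 9.5% |

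An average shift of 0.25 step arises, for example, if a quarter of one cohort's sera are read one step low (0.25 × 1).

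**Share at or above 1:40.** Under that quarter misreading, only sera truly at 1:40 cross the threshold, so loss = 0.25 × P(titer = 1:40). With titers rounded to the nearest step, median 1:40 and SD 1.0, P = 0.383 and the loss is 9.6 points.

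| Median | SD 1.0 | SD 1.5 | SD 2.0 |
|---|---|---|---|
| 1:40 | 9.6 | 6.5 | 4.9 |
| 1:80 | 6.0 | 5.3 | 4.4 |
| 1:160 | 1.5 | 2.8 | 3.0 |
| 1:320 | 0.1 | 0.9 | 1.6 |

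Exact enumeration of the planned chi-square/Fisher rule gives at most 6.6% rejection (median 1:40, SD 1.0), against 2.7% there without the shift. At SD 1.5 and the same median it is 5.1%. Every other combination in the table is below 5%.

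**Seroconversion, same misreading at both visits.** A shift common to both visits cancels in the four-fold-rise route only while the pre-vaccination reading stays at or above 1:10. A true <1:10 to 1:80 counts, but <1:10 to 1:40 does not. A true 1:10 to 1:40 counts, but read as <1:10 to 1:20 it does not. A true 1:20 to 1:80 counts either way. Simulation with pre-vaccination medians 1:10 to 1:40, pre-vaccination SD 1.5 or 2.0, median rises of 4- or 8-fold and SD of log2 rise 1.5 gives losses of 1.4 to 4.5 points, or 0.3 to 0.9 of 20 participants.

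**The case against.** The strongest reply is that the harm needs a second fact, that readers worked from the cohort-bearing label, and this is not documented. Section 11.10 answers a question about coding, not about assay masking. The HI method is delegated to cited studies and the neutralization method to a WHO protocol, and neither is available here. This stands as a limit. A reader might infer that titers were read unmasked, or that the results are biased; the documents support neither. But a general assay protocol would not by itself remove a letter that this study's own rule puts into the code.

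The letter also cannot always be known at the draw. The first antibody tube is taken at Screening Visit #1, while fasting glucose and lipids come at Screening Visit #2, so many participants cannot be classified until then. This is correct, but the code can still be applied before the assay.

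The effects are modest and depend on the inputs. A quarter of one cohort misread in one direction is a strong assumption, a tenth of a dilution hardly matters, and the threshold loss nearly vanishes when titers lie well above 1:40. All of this stands.

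**Conclusion.** The point holds as a gap in the plan. The stated rule puts the primary contrast into the code, and nothing in the available text removes it before the primary outcome is read. The size of any bias is unknown. Under the assumed shifts it ranges from negligible to a type I error of 12.0% for mean titers (quarter-step shift, SD 1.0). For proportions the main effect is a biased estimate rather than false positives: 0.1 to 9.6 points at the 1:40 threshold, with rejection only slightly above the nominal 5% in the worst case examined. This does not invalidate the design. It should be corrected before titers are read, because it cannot be repaired afterwards.

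**What to change.** Add to section 11.10: *Before the hemagglutination inhibition and neutralization assays, serum aliquots will be re-labelled with one sequential code assigned across both cohorts, showing no cohort. The coordinator keeps the linking log and releases it only after titers are locked. Staff who read titers have no access to the log.*

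Parent tube codes can stay as they are. This matters because tubes may already exist: Screening Visit #1-A refers to people screened earlier, and the RNA-seq text describes RNA as already obtained. Neither a plate-layout rule nor mid-study renumbering is needed for this point.

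The cost is re-labelling about 120 aliquots (40 participants × 3 listed antibody draws: Screening Visit #1, Day 28 and Day 90), or 200 (40 × 5) if Day 0 and Day 7 serum is also tested, plus custody of the log. Re-labelling carries a small mix-up risk, which the log controls. No visit, draw or assay is added. If aliquots are already re-coded before the assays, the plan need only say so.

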**12.2 \* Indicate the gender(s) of the subjects:**

Female

Male**12.3 \* Indicate projected enrollment by race and ethnicity. See Help for disease/volunteer population demographics.**

Ethnic Category	Sex/Gender		
	Females	Males	Total
Hispanic or Latino	6	5	11
Not Hispanic or Latino	15	14	29
Ethnic Category: Total of All Subjects*	21	19	40
Racial Categories			
American Indian/Alaska Native	0	0	0
Asian	3	2	5
Native Hawaiian or Other Pacific Islander	0	0	0
Black or African American	7	7	14
White	11	10	21
Racial Categories: Total of All Subjects*	21	19	40

**12.4 \* Will subjects of a specific racial/ethnic group be excluded from participation?** Yes  No

If Yes, please specify:

- Caucasian  
 African-American  
 Hispanic  
 Asian  
 Other

Reason for the exclusion:

- The condition being studied does not occur in the selected group(s)  
 Other

If Other, please specify:

**12.5 Gender/Minority Exclusion Justification**

All research involving human subjects should be designed and conducted to include members of both genders and members of minority groups, unless a rationale and justification is provided. Please provide such justification below:

**12.6 Vulnerable Populations**

Indicate whether any of the following populations will be included in the study:

- Children  
 Pregnant Women  
 Cognitively Impaired Persons  
 RU Employees  
 RU Students  
 Fetal Tissue or Embryonic Stem Cells  
 Induced Pluripotent Stem Cells  
 Other:

If you checked any of the above, give a brief explanation of the need to use these particular individuals:

Special precautions will be used in recruiting employees of the Rockefeller University to minimize the possibility of undue influence. Rockefeller University employees will be made aware of the study through flyers rather than directed presentation to selected groups. Subjects will be reassured that refusal to participate in the study will not affect their studies or employment in any way

If the subject is a Rockefeller University employee, does she/he work within the Laboratory of the Principal Investigator or Co-Investigator(s)?

- Yes  
 No  
 N/A

If the subject is a Rockefeller University student, does she/he work within the Laboratory of the Principal Investigator or Co-Investigator(s)?

- Yes  
 No  
 N/A

**12.7 \*What is the total number of evaluable participants you plan to enroll at Rockefeller University Hospital over the course of the entire study?**

40

**12.8 \* What is the total number of participants who will need to sign consent at Rockefeller University Hospital over the course of the entire study to result in the desired number of evaluable subjects?**

100

**12.9 \* What is the total number of participants you plan to sign consent at Rockefeller University Hospital in the next year?**

100

**12.10 \* What will be the total number of evaluable participants at all sites over the course of the entire study?**

40

**12.11 Inclusion Criteria**

Please list subject inclusion criteria:

**Order Number    Criteria**

**METABOLIC SYNDROME COHORT**

Any evidence of NHLBI Guidelines for Clinical Identification of the Metabolic Syndrome: (must have 3 or more of the following risk factors):

Abdominal Obesity, given as a waist circumference:

- Men >102 cm (>40 in)
- Women > 88 cm (>35 in)

Triglycerides  $\geq 150$  mg/dl

HDL Cholesterol:

- Men < 40 mg/dl
- Women <50 mg/dl

Blood Pressure  $\geq 130/ \geq 85$  mm Hg or on antihypertensive medication

Fasting Glucose  $\geq 100$  mg/dl

1

**HEALTHY CONTROLS**

BMI 18.5 - 25 kg/m^2

HDL female > 50 mg/dL, male > 40 mg/dL

fasting glucose < 100 mg/dL

triglycerides <150 mg/dL,

waist circumference of a female < 88 cm, male < 102 cm)

Blood pressure  $\leq 120/80$

2

May be on antihypertensive medication

**12.12 Exclusion Criteria**

Please list subject exclusion criteria:

**Order Number    Criteria**

1                      Currently undergoing treatment for the metabolic syndrome

2                      Blood Pressure > 150/90

- 3 NSAIDs and/or Aspirin ingestion within the last 14 days
- 4 Hepatitis A, B and C
- 4 Self-reported history of any active autoimmune diseases
- 5 Self-reported ingestion of statins within the last 3 months
- 6 Self-reported antibiotic use within the last 3 months
- 7 Anti-inflammatories including biologics and corticosteroids within last 3 months( nasal spray and topical applications are OK)or Omega 3 Fatty Acids.
- 8 Self-reported hx of cancer treatment within the last year
- 9 Allergy to eggs
- 10 History of Guillain-Barre syndrome
- 11 Pregnant ( determined by POCT at Screening visit #1 and Study visit #1).
- 12 HIV positive
- 13 Self-reported history of receiving the flu vaccination after June 1, 2016.
- 14 Any self-reported infection in the week of the visit except the first two visits (Screening visit 1 and Screening visit 2) and the last visit (Study visit #5) that could be rescheduled.
- 15 Any medical, psychological or social condition that, in the opinion of the Investigator, would jeopardize the health or well-being of the participant during any study procedures or the integrity of the data.

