**drawn prior to flu vaccine)**

POCT - urine pregnancy test

Adverse event assessment

Administration of the influenza vaccine intramuscularly (IM): Vaccination with quadrivalent 2016-2017 vaccine A/California/7/2009 (H1N1); A/Hong Kong/4801/2014 (H3N2); B/Brisbane/60/2008(B/Victoria lineage); B/Phuket/3073/2013 (B/Yamagata lineage). Participants of normal weight will be injected IM with a needle of 1 to 1.5 in length. Obese individuals (defined as BMI>25) generally will require the use of a 2 in length needle to assure that the injection reaches the muscle. The needle length used for injection will be documented in the medical record.

Total blood volume to be drawn for visit #1 = 26.5ml

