## 16.0 Recruitment and Advertising

**For assistance consult CRSO to create a robust Recruitment Plan see Help.**

### 16.1 \* What is the plan for recruitment?

**Overview:**

The CRROSS will prescreen up to 100 volunteers in order to enroll 20 with a metabolic syndrome and 20 healthy controls to achieve the goal of 40 evaluable participants at study completion. Healthy controls will be age matched (+/-5 years) and gender matched to the metabolic syndrome participants.

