**Projected enrollment timeline:** Recruitment initiation will begin as soon the study receives IRB approval, likely in the first or second week of November. The investigator's target of completing accrual by April 2016, which would allow for 5-6 months achieving complete study enrollment. This would require the enrollment of 10 participants (5 metabolic syndrome and 5 age matched controls) per month. The study requires 2 screening visits (1 week start-up lag). The enrollment timeline is ambitious, even assuming a steady flow of participants and likely only feasible using the Repository population and potentially expanding the age range. Based on previous recruitment experience of this population, CRROSS would predict 12- 15 months for study accrual, however given ResearchMatch and Repository resources, 6 months is ambitiously feasible.

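### Vaccination in the 2015-16 season is left out of eligibility, matching and analysis, although the comparison is non-randomised and has only 20 participants per cohort

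*Combined protocol and SAP*

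**What the plan says.** Section 12.12, no. 13, excludes volunteers with "Self-reported history of receiving the flu vaccination after June 1, 2016". No criterion concerns vaccination before that date.

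Section 16.1 (Overview) gives the matching rule: "Healthy controls will be age matched (+/-5 years) and gender matched to the metabolic syndrome participants". Vaccination history is not a matching factor.

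Section 11.9 (Statistical Analysis) compares mean titres by t-test or Wilcoxon-Mann-Whitney, and compares responder proportions by chi-square or Fisher's exact test. No covariate is named. Section 11.8 suggests two responder endpoints: the proportion reaching an HI titre of at least 1:40, and seroconversion, which is defined from both the pre- and post-vaccination titre.

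Screening Visit #1 (11.7) includes a general medical history and a baseline influenza antibody sample. No item on previous-season vaccination is named there.

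On timing, Study Visit #1 specifies "Vaccination with quadrivalent 2016-2017 vaccine", and the laboratory section of 11.7 says "Determine antibody titers against each strain of influenza included in the quadrivalent 2016-2017 vaccine". The recruitment timeline in 16.1 gives a "target of completing accrual by April 2016" and adds: "CRROSS would predict 12- 15 months for study accrual, however given ResearchMatch and Repository resources, 6 months is ambitiously feasible".

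**The concern.** The cohorts are formed by metabolic status, not by randomisation, so a factor that affects the antibody response can differ between them for reasons unrelated to metabolic syndrome. By excluding recent vaccinees, the plan already treats influenza vaccination history as relevant. It then stops at 1 June 2016. A volunteer entering in autumn 2016 may have been vaccinated in spring 2016 or at any earlier point in the 2015-16 season.

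The endpoints are exposed to different degrees:

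- **HI titre of at least 1:40.** Baseline plays no part. Someone already at 1:40 before Day 0 can count as a success without responding to the study vaccine.
- **Mean titre.** The planned test does not adjust for the pre-vaccination titre.
- **Seroconversion.** The pre-vaccination titre is part of the definition, so baseline is partly reflected. Vaccination history itself is not.

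At stake is a cohort difference that reflects who was vaccinated the year before, or a real difference hidden by it.

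**Working it through.** **The plan's own figures.** The plan gives no rate of previous-season vaccination and no effect of it, so there is nothing to reproduce on the main point. The only related figure is the accrual forecast of 12 to 15 months. The earlier study cited in 16.1 enrolled 28 in 2 years: 28/24 = 1.17 per month, so 20 metabolic syndrome participants would take 20/1.17 = 17.1 months. The forecast comes with no formula and reads as a judgement.

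**Inputs for the illustration.** From 11.9: 20 per cohort, 5% level, chi-square test, or Fisher's exact test if any observed frequency is below 5. Assumed, because the documents are silent: seroconversion of 60% without and 30% with previous-season vaccination, and no effect of metabolic syndrome.

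**Spurious difference.** Expected seroconversion in a cohort with coverage c is 0.30c + 0.60(1 − c). The difference between cohorts is therefore 0.30 × (coverage gap).

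- Coverage 30% v 40%: 0.30 × 0.30 + 0.70 × 0.60 = 0.51, against 0.40 × 0.30 + 0.60 × 0.60 = 0.48. Difference 3 points.
- Coverage 30% v 60%: 0.51, against 0.60 × 0.30 + 0.40 × 0.60 = 0.42. Difference 9 points.

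The sign follows whichever cohort was vaccinated more.

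**Rejection rate of the planned test.** This is an exact binomial enumeration over all outcomes at 20 v 20, with no true cohort effect.

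| Assumed seroconversion (without / with) | Coverage | Spurious difference | Rejection rate |
|---|---|---|---|
| 60% / 30% | balanced, 50% v 50% | 0 | 0.038 |
| 60% / 30% | 30% v 40% | 3 points | 0.042 |
| 60% / 30% | 30% v 60% | 9 points | 0.070 |
| 60% / 30% | 30% v 70% | 12 points | 0.096 |
| 60% / 40% | 40% v 60% | 4 points | 0.045 |
| 70% / 20% | 20% v 80% | 30 points | 0.44 |

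The last row is an extreme that nothing in the documents supports. It only marks the edge of the range.

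**Chance imbalance.** With equal true coverage in both cohorts, a gap of 20 points is 4 participants out of 20. The probability of a gap at least that large is 0.23 at 30% coverage and 0.27 at 50%.

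**Calendar check on the fixed date.**

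- Accrual of 12 to 15 months starting September to November 2016 ends between September 2017 and February 2018. By then the wording would also exclude people vaccinated in 2016-17.
- Counted from the initial IRB approval of 25 November 2015 (9.7), 12 to 15 months ends between 25 November 2016 and 25 February 2017, within the 2016-17 season. The rule's meaning does not change.
- Six months from September to November 2016 ends between March and May 2017. The meaning again does not change.

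**The case against.** A reader might infer that exclusion 13 will change its meaning partway through accrual, because the date is fixed and the plan mentions 12 to 15 months. The documents do not support this. The date fits a single-season design, since vaccine and assay strains are both fixed to 2016-2017. The sentence with the 12 to 15 months goes on to call 6 months ambitiously feasible. No section plans enrolment in autumn 2017, and the 3 years in 9.8 is study duration, not accrual. Enrolling in 2017-18 would require the vaccine and assay sections to be rewritten, and the date could be changed with them.

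A reader might also infer that fold-rise is the outcome and is wholly unprotected. It enters only seroconversion, which already uses the pre-vaccination titre. If earlier vaccination raises starting titres, the 1:40 endpoint could even move the opposite way from seroconversion.

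Other objections carry some weight. The effect of previous vaccination on response, and any difference in coverage between cohorts, are assumptions. Section 16.1 says many volunteers may not know they have metabolic syndrome, but that is not evidence on vaccination. A history is taken, applying no. 13 requires a question about influenza vaccination, and the table in 13.1 is cut off in the public copy, so the information may be partly collected. Modest imbalance barely moves the rejection rate.

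What these objections leave standing is that previous-season vaccination is absent from the eligibility criteria, the matching factors and the named analyses.

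**Conclusion.** The gap is real but moderate. In a non-randomised comparison of 20 v 20, 2015-16 vaccinees are eligible and no stated step accounts for them. The HI 1:40 proportion and the mean titre have no protection, and seroconversion has partial protection. Under the assumed 60% and 30% seroconversion rates, plausible coverage gaps of 10 to 30 points give spurious differences of 3 to 9 points. The main harm is a biased estimate in either direction; the false-positive rate rises little. The true size cannot be derived from the documents. The change is worth making because it is cheap and because the history is harder to recover reliably later.

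The fixed date becomes a problem only if accrual passes the 2016-17 season. Separately, the April 2016 accrual target in 16.1 precedes both the 1 June 2016 cut-off and the 2016-2017 vaccine, and these sections must be reconciled.

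**What to change.** 1. At Screening Visit #1, record influenza vaccination in the previous season (yes/no and month), and report it by cohort.
2. In 11.9, keep the planned tests and add at least one prespecified adjusted analysis of titres and of responder status, with previous-season vaccination and baseline titre as covariates or strata. For titres, regress the log post-vaccination titre on cohort, log baseline titre and previous-season vaccination. For the binary endpoints, a stratified or penalised method suits 20 per cohort better than ordinary logistic regression.
3. If accrual runs past the 2016-17 season, revise the date in no. 13 and the fixed vaccine and assay strains in 11.7 together, and include season in the comparison.
4. Reconcile the April 2016 accrual target in 16.1 with the June 2016 cut-off and the 2016-2017 vaccine.

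The cost is one question and one or two model terms: a lost degree of freedom or two, and some error from self-report. No extra visit, blood draw or participant is needed.
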